5.10.5 Vital Signs, Physical Examination and ECG

Over-time summary statistics (n, mean, SD, median and range) of vital signs (temperature, heart rate, respiratory rate, and systolic/diastolic blood pressure) will be provided for each scheduled visit. A separate summary will be produced for vital signs at baseline, maximum, minimum, change to maximum, change to minimum, last value, and change to last value.

Baseline physical examination findings will be summarized. New or worsened physical examination abnormalities will be analyzed as adverse events (AEs).

Descriptive statistics of ECG parameters (heart rate, PR interval, QRS interval, QT interval, and QT_C interval) will be presented.

5.11 Other Analyses

5.11.1 Pharmacokinetics

Plasma concentration-time data for Neihulizumab will be summarized by nominal time using descriptive statistics. For presentation of the individual data and summary statistics, concentrations below the limit of quantitation (BLQ) will be set to zero.

Patients who are considered as not evaluable will be listed with their individual plasma concentrations and individual pharmacokinetic parameters, however, will not be included in descriptive statistics for plasma concentrations, pharmacokinetic parameters or other statistical assessment. A patient is not evaluable if the patient has a protocol violation relevant to the evaluation of pharmacokinetics.

The PK parameters derived using non-compartmental techniques in Phoenix™ WinNonlin® (Version 8.0 or higher, Certara USA, Inc., Princeton, NJ). The following PK parameters will be assessed (other parameters at the discretion of the PK Scientist):

- C_{max} : The observed peak drug concentration
- C_{trough} : The residual drug concentration

The above PK parameters will be summarized using descriptive statistics (n, arithmetic mean, SD, minimum, median, maximum, arithmetic coefficient of variation, geometric mean, geometric coefficient of variation). Geometric means and between-patient coefficients of variation (CV_b) will be calculated for \log_e -transformed C_{trough} and C_{max} where:

$$\text{Geometric mean} = \exp(\text{mean on log scale})$$

$$CV_b (\%) = \sqrt{\exp(SD^2) - 1} \times 100,$$

where: SD is the standard deviation of the \log_e -transformed data.

Mean plasma concentration-time data will be presented graphically on linear and semi-logarithmic scales using nominal time. Individual concentration-time data and graph of C_{trough} will be presented for all patients plotted grouped together on linear and semi-logarithmic scales using nominal times. No data monitoring committee (DMC) review meetings are planned. However, Primary internal data monitoring will be performed continuously over the accrual and follow-up periods by the site PI and the Study Coordinator.

5.11.2 Quality of Life

To examine the quality of life in the patient population, a self-administered IBD questionnaire containing 32 questions identifiable to four dimensions: systemic symptoms (S), bowel symptoms (B), social Function (SF), and emotional function (E) will be used. The score of the questionnaire will be used to determine subjective health status for patients with inflammatory bowel disease over time.

IBDQ four dimensions:

- Bowel symptoms (B) – Question #s: 1, 5, 9, 13, 17, 20, 22, 24, 26, and 29
- Emotional function(E) – Question #s: 3, 7, 11, 15, 19, 21, 23, 25, 27, 30, 31, 32
- Systemic symptoms (S) – Question #s: 2, 6, 10, 14, 18
- Social function (SF) –Question #s: 4, 8, 12, 16, and 28.

The scoring of each question is in 1-7 scale. The higher the score the less quality of life is impaired. The IBDQ is calculated by summing the score of each question resulting in a maximum 224 and minimum of 32. If >50% of the questions are left unanswered the total will be treated as missing. The IBDQ questions with above 4 dimensions will be given in the Appendix 1.

Total IBDQ and the change of it from baseline will be summarized by each visit (Baseline, Week 12, and EOS/Week 26) using descriptive statistics. The number and proportion of patients with total IBDQ increased at least 16 points from baseline will also be summarized. Improvement or deterioration of each dimension from baseline to EOT will be compared using paired t-test. By subject listings of these data should be provided.

5.12 Immunogenicity (Anti-drug Antibody)

Results of ADA concentration will be described in the bioanalytical report, which will be included as an appendix in the final clinical study report.

5.13 Data Monitoring Plan

No data monitoring committee (DMC) review meetings are planned. However, Primary internal data monitoring will be performed continuously over the accrual and follow-up periods by the site PI and the Study Coordinator.

5.14 Determination of Sample Size

The primary endpoint is overall responsive rate at Day 84. Assuming placebo effects of 25% (historical data) and AbGn-168H responsive rate of 45%, 40 patients have > 80% power to detect an alpha of 0.1 (two sided).

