Name of finished product: Neihulizumab			
Name of active ingredient: AbGn-168H			
Protocol date (Original): 2017.09.26	Trial number: 2017.008.01		Revision date (Amendment 4): 2018.11.01
Criteria for safety:	Physical examination, vital signs, safety laboratory tests, adverse events and tolerability.		
Pharmacokinetics parameters:	C _{max} and associated parameters		
Immunogenicity:	The Immunogenicity (anti-drug antibody; ADA) of AbGn-168H will be evaluated by a qualitative bridging immunoassay with electrochemiluminescence detection.		
Statistical methods:	
Determination of sample size: Assuming placebo effects of 25% (historical data) and AbGn-168H responsive rate of 45%, 40 patients have > 80% power to detect an alpha of 0.1 (two sided).
 
All patients who receive AbGn-168H treatment (modified Intent to Treat set, mITT) will be included in all analyses.
 
Summaries of patient disposition, demographics, disease characteristics, assessments of physical condition and functionality. Summary statistics for the time from the first dosing date to the last dosing date will be provided as the extent of drug exposure.
 
Descriptive statistics with appropriate plots will be employed in the analysis of all efficacy, PK, PD biomarkers (Fecal calprotectin and CRP), and immunogenicity (ADA) data.
 
AEs will be listed by body system using MedDRA terms. Descriptive statistics will be provided for clinical laboratory test results by scheduled time of evaluation, as well as for the change from baseline.
 
Summary statistics of continuous variables including numbers, means, standard deviations, median, minimum and maximum will be calculated. Categorical variables will be presented as number and percentages.
		

CLINICAL STUDY PROTOCOL APPROVAL/ACKNOWLEDGMENT

APPROVAL STATEMENT OF ABGENOMICS

On behalf of AbGenomics, only the Sponsor Medical Monitor is authorized to approve the Clinical Study Protocol and any subsequent amendment(s).

The following person has approved this Clinical Study Protocol using signatures as presented below:

[name]

Sponsor Medical Monitor's Name (Print)

31 Oct 2018

Sponsor Medical Monitor's Signature

Date of Signature
(DD MMM YYYY)

APPROVAL STATEMENT OF THE LEAD INVESTIGATOR

It is the responsibility of the Lead Investigator to approve the Clinical Study Protocol and any subsequent amendment(s).

The following person has approved this Clinical Study Protocol using signatures as presented below:

[name]

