7.1.3 Efficacy analyses

Efficacy analyses will be performed based on the mITT set.

Summary statistics for efficacy endpoints will be provided.

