7.3 DETERMINATION OF SAMPLE SIZE

The primary endpoint is overall responsive rate at Day 84. Assuming Neihulizumab has a responsive rate of 44.6% (6.8 % higher than conventional treatment and 20% higher than control rate), 40 patients in Neihulizumab treatment is estimated to have > 80% power to detect the difference with a 1 sided significance level of $\alpha = 0.1$

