5.2 General Presentation Considerations

Due to the small number of patients expected to be enrolled at each center, all summaries and analyses will be performed using pooled patients across centers.

Unless otherwise specified, continuous data will be summarized with the number of non-missing observations, in terms of the mean, standard deviation (SD), median, minimum, maximum and number of observations, unless otherwise stated. Continuous data that are expected to be skewed will be presented in terms of the maximum, upper quartile, median, lower quartile, minimum and number of observations. The minimum and maximum will be reported to the same number of decimal places as the raw data recorded in the database. The mean, median, lower quartile and upper quartile will be reported to one more decimal place than the raw data recorded in the database. The SD will be reported to two more decimal places than the raw data recorded in the database. In general, the maximum number of decimal places reported shall be four for any summary statistic.

Categorical data will be summarized in terms of the number of patients providing data at the relevant time point (n), frequency counts and percentages.

Percentages will be presented to one decimal place. Percentages will not be presented for zero counts.

Confidence intervals will be presented to one more decimal place than the raw data.

The patients enrolled under Protocol amendments 1-3 were administered 8 doses of study medication over 11 weeks whereas the patients enrolled under amendment 4 will be administered

10 doses over 12 weeks. Therefore, the statistical analyses and summary tables will be performed by following groups: Group 1: the patients enrolled under amendments 1 to 3, Group 2: the patients enrolled under amendment 4.

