5.5.2 Visit Windows

‘Baseline’ is defined as the last available pre-treatment assessment. ‘End of Study’ is defined as the last available post-treatment assessment. ‘Treatment Day’ will be calculated relative to the date of first dose i.e. Treatment Day = Assessment Date –First dose date + 1.

The visit windows and study relative days are given in below table. Assessments at early termination and any deviation of scheduled visits will be slotted based on the following visit window but unscheduled visits will not be slotted to analysis visit as below.

Period	Analysis Visit Protocol Amendments 1-4	Analysis Visit Protocol Amendments 1-3	Analysis Visit Protocol Amendment 4	Target day (relative to first dose date)	Study Day** ranges
Screening Period	Week -4 to -1	Week -4 to -1	Week -4 to -1		-28 to -1
Treatment Period	Week 0	Week 0	Week 0	1	<=1
	Week 1	Week 1	Week 1	8	2-11
	Week 2	Week 2	Week 2	15	12-18
	Week 3	Week 3	Week 3	22	19-25
	Week 4	Week 4	Week 4	29	26-32
	Week 5		Week 5	36	33-39
	Week 6	Week 6	Week 6	43	40-47
	Week 7		Week 7	50	48-53
	Week 8	Week 8		57	54-60
	Week 9		Week 9	64	61-67
EOT	Week 12	Week 12	Week 12	84	82-104
Follow-up	Week 16	Week 16	Week 16	112	105-132
	Week 20	Week 20	Week 20	140	133-174
EOS	Week 26	Week 26	Week 26	182	175-212

**Study Day=Visit Date-First dose Date+1

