5.9.2 Primary Efficacy Endpoint

The primary efficacy endpoint is the proportion of clinical responders at week 12. The clinical response is a composite measurement of MCS and the rectal bleeding score. It is defined as:

a) ≥ 3-point reduction in MCS, a 30% or greater decrease from the baseline score,

AND

b) 1-point or greater decrease of the rectal bleeding subscale or an absolute rectal bleeding score of 0 or 1 at Week 12.

The proportion of response rate will be summarized with frequencies and percentages along with 2-sided 95% exact Clopper-Pearson confidence interval at Week 12.

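### The >80% power for 40 patients is tied to a one-sided 0.10 level in one place and a two-sided 0.10 level in two others, and it belongs to a pooled one-sample test that no document plans

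*SAP*

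**What the plan says.** Three current statements give more than 80% power for 40 patients.

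- Protocol 7.3 assumes a 44.6% response rate ("6.8 % higher than conventional treatment and 20% higher than control rate"), and 40 patients "is estimated to have > 80% power to detect the difference with a 1 sided significance level of" 0.1.
- The protocol synopsis, under statistical methods, begins "Assuming placebo effects of 25% (historical data) and AbGn-168H responsive rate of 45" per cent and sets alpha at 0.1 two-sided.
- SAP 5.14 repeats the synopsis: "40 patients have > 80% power to detect an alpha of 0.1 (two sided").

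None of them names the test.

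The analysis sections plan something else. Protocol 7.1.3 says only: "Summary statistics for efficacy endpoints will be provided". SAP 5.9.2 says that the Week 12 response rate "will be summarized with frequencies and percentages along with 2-sided 95% exact Clopper-Pearson confidence interval at Week 12", and gives no reference rate or success rule. SAP 5.2 splits the reporting by dosing regimen: "the statistical analyses and summary tables will be performed by following groups: Group 1: the patients enrolled under amendments 1 to 3", with Group 2 being those enrolled under amendment 4. The only pooling that SAP 5.2 states is across centers. SAP 4.1 reports that the study was closed out after slow enrollment and a pandemic hold, and that the available data will be analyzed. It gives no final number of patients and no group sizes.

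**The concern.** One design cannot carry both a one-sided and a two-sided 0.10 level. One puts 0.10 in the upper tail and the other 0.05. The primary objective is efficacy and the analysis sections set no benchmark, so the sample-size text is the only place that supplies one, and it exists in two versions. Someone writing the study report could cite either.

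The second problem is that SAP 5.14 restates the power without qualification in the document that splits the analysis by regimen and records early close-out. A reader could take the >80% as a property of the by-group 95% intervals, which it is not. What is at stake is how the result is described, not the estimate.

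**Working it through.** **Inputs.** n = 40. From the synopsis and SAP 5.14: null p0 = 0.25, target p1 = 0.45. From protocol 7.3: p1 = 0.446, and reading the 20% as absolute points, p0 = 0.446 − 0.20 = 0.246. The implied conventional rate is 0.446 − 0.068 = 0.378.

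**Reproducing the >80% (25% vs 45%, two-sided 0.10, z = 1.645).** The standard errors are √(0.25·0.75/40) = 0.0685 under the null and √(0.45·0.55/40) = 0.0787 under the target.

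- Null variance at the bar: Φ((0.20 − 1.645·0.0685)/0.0787) = Φ(1.11) = 86.7%.
- Target variance throughout: Φ(0.20/0.0787 − 1.645) = Φ(0.90) = 81.5%.

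At one-sided 0.10 (z = 1.282), the first formula gives 92.3%. With protocol 7.3's own rates it gives 92.4%. So >80% reproduces under either sidedness.

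**Which comparison it must be.** Read as two arms of 40, 25% vs 45% gives 59.3% two-sided and 72.8% one-sided. One-sample against the implied conventional rate (37.8% vs 44.6%) gives 35.0% one-sided. Only a one-sample test of all 40 against the control rate exceeds 80%.

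**Exact test.** The bar is the smallest k with P(X ≥ k | p0) no larger than the tail area, and power is P(X ≥ k | p1).

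- At p0 = 0.25 the upper tails are 0.1032 (k = 14), 0.0544 (15) and 0.0262 (16).
- At p0 = 0.246 they are 0.0927 (14) and 0.0480 (15).

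| Null / target | One-sided 0.10 | Two-sided 0.10, equal tails |
|---|---|---|
| 25% / 45% | ≥15/40, power 86.7% | ≥16/40, power 78.6% |
| 24.6% / 44.6% | ≥14/40, power 91.8% | ≥15/40, power 85.6% |

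Across a row, sidedness moves the bar by one patient. Down a column, the 0.4-point difference in null rate does the same. The choice of test matters too: at 25%, 15/40 passes a two-sided score test (z = 0.125/0.0685 = 1.83, p = 0.068) but misses the equal-tailed exact rule (0.0544 > 0.05) and the Wald test (z = 1.63, p = 0.102).

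**The planned interval.** The SAP does not compare its 95% interval with any rate. If it were read against 25%, the lower limit is 24.9% at 16/40 and 27.0% at 17/40. The bar is therefore 17/40, with power 68.1% at a true 45%. At n = 30 the bar is 13/30 and power 64.1%. Read against 24.6% with a 44.6% target, power is 77.1% at n = 40 and 62.4% at n = 30. Group sizes are not given; at assumed sizes of 20 and 10, the 25% / 45% reading gives 40.9% and 26.2%.

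**Possible source of the rates.** Protocol Table 3A (anti-TNF-exposed, induction response) lists placebo rates of 28.7% and 20.6%, averaging 24.65%, and active rates of 36.7% and 39.0%, averaging 37.85%. These fit protocol 7.3's implied 24.6% and 37.8% to within 0.05 point. The documents do not state this derivation.

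**The case against.** The best defence is that the power statement is a design-stage figure for a planned 40 patients, and as such it is sound by normal approximation. A descriptive phase II analysis is legitimate and openly stated. An exact interval can be set against any rate, including those in Table 3A. The regimen split came with an amendment and does not undermine the design calculation. No success rule exists for the sample-size text to alter, and with the study closed out no enrollment decision depends on it. All of this stands, and it is why the point is minor.

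It can also be said that a combined analysis is not ruled out. SAP 5.5.2 has a column headed "Analysis Visit Protocol Amendments 1-4", SAP 5.9.1.1 sets its missing-data threshold over all patients, and SAP 5.9.3 plans plots for the mITT population. These are hints. None specifies a pooled primary estimate, and none names a test.

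Two stronger readings are tempting. A reader might infer that the >80% is miscalculated. The documents do not support that, since only an equal-tailed exact or Wald rule at 25% vs 45% falls below 80%, and then only to 78.6%. A reader might also compare the statements at 14/40, which passes protocol 7.3's test and fails SAP 5.14's, and blame sidedness alone. That comparison changes the null rate as well. Under the exact test, 14/40 already misses a one-sided 0.10 level at 25% (0.1032).

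**Conclusion.** The conflict is literal and lies within current text. At 25% vs 45%, sidedness moves the exact bar from 15/40 to 16/40 and the power from 86.7% to 78.6%. The difference in null rate is worth another patient. Separately, the >80% in SAP 5.14 is not a property of the planned analysis. Even pooled, a 95% interval read against 25% would have 68.1% power at 40 patients and 64.1% at 30, and less within groups.

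These figures assume a one-sample binomial comparison, the absolute reading of the 20% in protocol 7.3, and, for the interval, a decision rule that the SAP does not contain. The group figures also rest on assumed sizes. It would go too far to conclude that the primary analysis is invalid or underpowered, because it is an estimate with an exact interval, fully specified and unaffected. Nor do the documents show which sidedness was intended: two statements against one is not evidence of that. Severity: minor.

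**What to change.** 1. Reconcile the synopsis, protocol 7.3 and SAP 5.14 to one null rate, target rate, alpha and sidedness. The sponsor should confirm which set was used for the design. State the source of the historical rate, and if it is Table 3A, say so.
2. In SAP 5.14, label >80% as a design-stage, normal-approximation figure for a pooled one-sample test at n = 40. Give the exact power for the confirmed inputs beside it (for example, 78.6% for equal-tailed exact two-sided 0.10 at 25% vs 45%). State that no such test is performed and that the by-group 95% intervals at the close-out N do not carry that power.

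Optional: report the expected interval width at the actual N, or add a pooled exact 90% interval. The latter would have to be marked as specified after close-out and as mixing the 8-dose and 10-dose regimens.

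The cost is wording only, with no new data or patients. The stated power becomes slightly less favourable if the exact two-sided figure applies.

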Appendix 1: IBDQ Questionnaire Summary

Appendix: Inflammatory Bowel Disease Questionnaire (IBDQ) Summary

The IBDQ includes 32 questions. The wording is deliberately repetitious, as experience has taught us that the repetition ensures subjects' understanding. The questions are grouped into four categories: bowel symptoms (B), systemic symptoms (S), emotional function (E), and social function (SF). Response options are consistently presented as seven-point scales. An example of the way the questions are structured follows:

(B) 1. How frequent have your bowel movements been during the last two weeks? Please indicate how frequent your bowel movements have been during the last two weeks by picking one of the options from the WHITE card in front of you.

- 1 BOWEL MOVEMENTS AS OR MORE FREQUENT THAN THEY HAVE EVER BEEN
- 2 EXTREMELY FREQUENT
- 3 VERY FREQUENT
- 4 MODERATE INCREASE IN FREQUENCY OF BOWEL MOVEMENTS
- 5 SOME INCREASE IN FREQUENCY OF BOWEL MOVEMENTS
- 6 SLIGHT INCREASE IN FREQUENCY OF BOWEL MOVEMENTS
- 7 NORMAL, NO INCREASE IN FREQUENCY OF BOWEL MOVEMENTS

(S) 14. How often during the last two weeks have you had problems getting a good night's sleep, or been troubled by waking up during the night?

(E) 15. How often during the last two weeks have you felt depressed or discouraged?

(SF) 16. How often during the last two weeks have you had to avoid attending events where there was no washroom close at hand?

(B) 17. Overall, in the last two weeks, how much of a problem have you had with passing large amounts of gas?

(S) 18. Overall, in the last two weeks, how much of a problem have you had maintaining, or getting to, the weight you would like to be at?

(E) 19. Many patients with bowel problems often have worries and anxieties related to their illness. These include worries about getting cancer, worries about never feeling any better, and worries about have a relapse. In general, how often during the last two weeks have you had felt worried or anxious?

(B) 20. How much of the time during the last two weeks have you been troubled by a feeling of abdominal bloating?

(E) 21. How often during the last two weeks have you felt relaxed and free of tension?

(B) 22. How much of the time during the last two weeks

The working structure of the other questions is identical, and appropriate seven-point scales are offered for each question. The content of the remaining 31 questions is as follows:

- (S) 2. How often has the feeling of fatigue or of being tired and worn out been a problem for you during the last two weeks?
- (E) 3. How often during the last two weeks have you felt frustrated, impatient, or restless?
- (SF) 4. How often during the last two weeks have you been unable to attend school or work because of your bowel problem?
- (B) 5. How much of the time during the last two weeks have your bowel movements been loose?
- (S) 6. How much energy have you had during the last two weeks?
- (E) 7. How often during the last two weeks did you feel worried about the possibility of needing to have surgery because of your bowel problem?
- (SF) 8. How often during the last two weeks have you had to delay or cancel a social engagement because of your bowel problem?
- (B) 9. How often during the last two weeks have you been troubled by cramps in your abdomen?
- (S) 10. How often during the last two weeks have you felt generally unwell?
- (E) 11. How often during the last two weeks have you been troubled because of fear of not finding a washroom?
- (SF) 12. How much difficulty have you had, as a result of your bowel problems, doing leisure or sports activities you would have liked to have done during the last two weeks?
- (B) 13. How often during the last two weeks have you been troubled by pain in the abdomen?

have you had a problem with rectal bleeding with your bowel movements?

(E) 23. How much of the time during the last two weeks have you felt embarrassed as a result of your bowel problem?

(B) 24. How much of the time during the last two weeks have you been troubled by a feeling of having to go to the bathroom even though your bowels are empty?

(E) 25. How much of the time during the last two weeks have you felt tearful or upset?

(B) 26. How much of the time during the last two weeks have you been troubled by accidental soiling of your underpants?

(E) 27. How much of the time during the last two weeks have you felt angry as a result of your bowel problem?

(SF) 28. To what extent has your bowel problem limited sexual activity during the last two weeks?

(B) 29. How much of the time during the last two weeks have you been troubled by feeling sick to your stomach?

(E) 30. How much of the time during the last two weeks have you felt irritable?

(E) 31. How often during the last two weeks have you felt lack of understanding from others?

(E) 32. How satisfied, happy, or pleased have you been with your personal life during the past two weeks?

